- Next recommended dose by the BLRM = current dose
- At least 12 subjects have been treated in the trial
- At least 6 subjects have been treated at the MFD

Part B of the study will only start if the highest dose is tolerated. Once the last subject in the highest dose cohort of Part A has attended visit 5 (day15) the SMC will meet and evaluate all

DLE data as well as available systemic and ophthalmological safety data. The decision on whether to proceed to Part B will be taken based on the occurrence of DLEs.

Part B:

In Part B, the highest dose will be used (██████). Thirty subjects will be recruited, 2:1 ratio of active treatment versus sham. Subjects dosed in Part A of the trial will not be included.

Subjects will be randomized to receive either active treatment or sham injection.

In Part B, subjects will receive three consecutive doses/sham injections over a 3-month period (██████████). All subjects included in the part B of the trial, will be observed for safety and efficacy for 12 weeks after the last injection.

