3.2 DISCUSSION OF TRIAL DESIGN, INCLUDING THE CHOICE OF CONTROL GROUP(S)

This trial is designed to confirm that the highest dose of BI765128 can be used for further testing in phase IIb trials. The trial consists of separate parts, A and B. The SRD dose escalation part is included and was designed with the goal to minimize the number of subjects exposed to subtherapeutic doses while on the other hand preserving safety and rapid dose finding. This part of the trial will enrol subjects with DMI as IVT injections in healthy subjects would not be considered ethical. Dose escalation and cohort size will be decided by the SMC, guided by a BLRM with overdose control. An EWOC design will increase the chance of treating subjects at efficacious doses while reducing the risk of overdosing. The use of BLRM for Phase I studies has also been advocated by the European Medicines Agency (EMA) guideline on small populations [[R07-4856](#)] and by the Food and Drug Administration (FDA) [[R13-4881](#)].

Part B will consist of a MD cohort [REDACTED] and will start after Part A. Subjects will either be randomized to the active treatment group or to a sham control group (ratio 2:1). This part of the trial will generate additional safety data after multiple dosing and allow for exploration of the time course and durability of treatment effects. This data will further inform the injection frequency and intervals in later studies.

An extended SMC will be established for both part A and part B. The SMC shall operate under the principles specified in the SMC charter. The primary objective of the SMC is to ensure and protect the safety and well-being of the trial subjects and to regularly review the trial data and provide recommendation for the further conduct of the trial (see section [8.7](#)).

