4.1.3 Method of assigning subjects to treatment groups

After the assessment of all in- and exclusion criteria, subjects will be enrolled into the Part A and Part B. Recruitment in the trial will start with the lowest dose group of Part A. Part B will recruit subjects only after Part A has been completed and safety of the doses has been established.

In Part A, the dose is planned to be escalated in cohorts at the pre-defined provisional dose levels; see Table 4.1.2: 1. Intermediate or lower dose levels, depending on the number of DLEs observed in the study, as long as they fulfil the EWOC criterion, may be investigated if agreed upon between Investigator and Sponsor. At the end of each treatment cohort, BI will convene a meeting with the SMC members. At the dose escalation meeting, all available systemic and ophthalmological safety data (See section 3.1 and 5.2.1) will be reviewed in

detail. Based on that and on the results of the updated BLRM, a decision on the next dose level to be tested is made.

In general, recruitment for Part A will be done successively for the dose groups, i.e. if the required number of subjects for one dose group is completed and this dose is considered safe based on (the BLRM model and the clinical course), the recruitment of the next higher dose group may be started. Therefore, the recruitment of subjects for the dose groups will neither be influenced by the trial personnel nor by any characteristics of the subjects, but only by temporal availability. Subjects from the Part A are not allowed to participate in Part B.

The highest dose (██████), if established as safe and tolerable during Part A will be used in Part B after Part A has been completed. If the highest dose (██████) is not considered safe and tolerable Part B will not commence. In Part B subjects will be randomized to receive either active IVT treatment or sham injection according to a randomization plan at visit 2 via Interactive Response Technology (IRT). 20 subjects will receive IVT treatment and 10 will receive sham injection.

The randomization procedure is described in Section [7.5](#).

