7.1 STATISTICAL DESIGN – MODEL

This trial will consist of a Part A followed by a Part B. The Part A will be conducted non-randomized, open-label, and uncontrolled. Part B will be conducted double-masked randomized and sham-controlled.

Part A:

The dose escalation will be guided by a Bayesian 2-parameter logistic regression model with overdose control [R13-4803, R13-4806].

The model is given as follows:

$$\text{logit}(\pi_d) = \log(\alpha) + \beta \cdot \log(d/d^*),$$

where $\text{logit}(\pi) = \log(\pi/(1-\pi))$, π_d represents the probability of having a DLE in the evaluation period at dose d , $d^* = \blacksquare$ mg is the reference dose, allowing for the interpretation of α as the odds of a DLE at dose d^* , and $\theta = (\log(\alpha), \log(\beta))$ with $\alpha, \beta > 0$ is the parameter vector of the model.

The estimated probability of a DLE at each dose level from the model will be summarized using the following intervals:

Target toxicity: [0.00, 0.25)

Over toxicity: [0.25, 1.00]

The BLRM-recommended dose for the next cohort is the highest dose level with posterior probability of the DLE rate falling in the target interval [0.00, 0.25) among the doses fulfilling EWOC. Thus, applying the EWOC criterion it should be unlikely (< 25% posterior probability) that the DLE rate at that dose will exceed 0.25. However, the allowed dose increment will always be the next higher pre-planned dose. However, the maximum allowable dose increment for the subsequent cohort will be no more than 250% from the previous dose. Dose escalation will continue up to the \blacksquare dose as long as the EWOC criterion for the next dose level is fulfilled. At the final dose, at least 6 treated subjects are required. However, the SMC may decide to include additional number of subjects at this dose level.

Since a Bayesian approach is applied, a prior distribution $f(\theta)$ for the unknown parameter vector θ needs to be specified. This prior distribution will be specified as a mixture of three multivariate normal distributions, i.e.

$$f(\theta) = a_1 f_1(\theta) + a_2 f_2(\theta) + a_3 f_3(\theta)$$

with a_i , $i = 1, 2, 3$ the prior mixture weights ($a_1 + a_2 + a_3 = 1$), and $f_i(\theta) = \text{MVN}(\mu_i, \Sigma_i)$, the multivariate normal distribution of the i -th component with mean vector μ_i and covariance matrix Σ_i , where

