It was then assessed how often a dose was declared as MFD with true DLE rate in the targeted or in the overdosing range. Furthermore, the average, minimum and maximum number of subjects per trial and the average number of DLEs per trial are reported. Results are shown in Table 10.3: 3.

Table 10.3: 3 Simulated operating characteristics

Scenario	% of trials declaring a MFD with true DLE rate in		% of stopped trials*	# Subjects	# DLEs
		overdosing		Mean (Min-Max)	Mean (Min-Max)
1	94.1	2.0	3.9	10.99 (3 - 27)	1.21 (0 - 6)
2	76.2	0.6	23.2	11.39 (3 - 27)	2.14 (0 - 8)
3	99.0	0.8	0.2	9.32 (9 - 27)	0.33 (0 - 5)
4	15.1	18.1	66.8	10.10 (3 - 27)	3.40 (0 - 7)
5	99.9	0.0	0.1	11.84 (9 - 27)	1.37 (0 - 5)

* The stopped trials include early stopped trials (stopped due to too much toxicity), as well as trials that stopped because the maximum allowed subject number was reached before an MFD was found.

In scenario 1, which reflects the case that the true dose-toxicity is aligned with prior mean, 94.1% of the simulated trials declared a dose as MFD with true DLE rate in the targeted toxicity range. Note that 3.9% of the simulated trials stopped either because there was no MFD determined after 27 subjects had been observed or because of too high toxicity for the planned doses.

In scenario 2, the assumed dose toxicities is high. This results in a higher percentage of early stopped trials (about 23.2 %). In this case, about 76.2 % of the trials would end with an estimated MFD within the targeted range, and 0.6 % in the overdosing range.

In Scenario 3 (low-toxicity scenario), only 99.0 % of the trials declared a dose as MFD with true DLE rate in the targeted range. In 0.8 % of the trials, the estimated MFD was in the overdosing range.

Scenario 4 (very-high-toxicity scenario) shows the worst results, i.e. the highest number of stopped trials (66.8 %) and a low number of trials with estimated MFD (15.1 %) in the target range, as would be expected.

Scenarios 5 (low-high toxicity scenario) shows the best results, i.e. the lowest number of stopped trials (0.1 %) and a highest number of trials with estimated MFD (99.9 %) in the target range.

The mean subject numbers ranged from 9.3 subjects (Scenario 3) to 11.8 subjects (Scenario 5), and the maximum number of subjects was 27.

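### Table 10.3:3 counts an MFD at any acceptable dose as a success, although Part B can start only at the highest dose; how often the highest dose is declared is not reported

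*Protocol*

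**What the plan says.** Part A gates Part B on one dose. Protocol 3.1: "Part B of the study will only start if the highest dose is tolerated", and "The decision on whether to proceed to Part B will be taken based on the occurrence of DLEs". Protocol 4.1.3 says that if the highest dose "is not considered safe and tolerable Part B will not commence". Protocol 3.2 gives the purpose: "This trial is designed to confirm that the highest dose of BI765128 can be used for further testing in phase IIb trials". No section lets Part B run at a lower dose.

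The model rule is in 7.1. Under EWOC "it should be unlikely (< 25% posterior probability) that the DLE rate at that dose will exceed 0.25". On step size, "However, the allowed dose increment will always be the next higher pre-planned dose", with a 250% limit on the increment. The final dose needs at least 6 treated subjects. The MFD may be considered reached with at least 12 subjects in total, at least 6 at that dose, and the model recommending the current dose again.

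The metric in 10.3 is different: "It was then assessed how often a dose was declared as MFD with true DLE rate in the targeted or in the overdosing range". Table 10.3:3 prints 94.1, 76.2, 99.0, 15.1 and 99.9% in the target range for scenarios 1 to 5. The text then says of one of them: "Scenarios 5 (low-high toxicity scenario) shows the best results, i.e. the lowest number of stopped trials (0.1" %). Protocol 7.6 calls the operating characteristics for the MFD recommendation reasonable on the strength of this simulation.

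**The concern.** Table 10.3:2 gives these true DLE rates at the three planned doses:

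- Scenario 1: 0.054, 0.073, 0.153
- Scenario 2: 0.154, 0.173, 0.243
- Scenario 3: 0.005, 0.007, 0.053
- Scenario 5: 0.005, 0.007, 0.243

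All twelve are below 0.25. In these four scenarios an MFD at the lowest or middle dose is therefore scored the same as an MFD at the highest, yet only the highest leads to Part B. The share of trials in which an acceptable highest dose is not the one declared appears nowhere in 10.3 or 7.6. Someone judging whether Part A is large enough for its go/no-go decision has only figures that answer another question.

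**Working it through.** **Inputs.** The three-component prior is in Table 7.1:1, the true rates in Table 10.3:2, and the rules in 3.1, 7.1 and 10.3. Doses are redacted, so only ratios to the reference dose can be used. The first prior component has mean log(α) = −2.197 = logit(0.1), and 0.1 is the assumed median rate at the maximum dose; the reference dose is therefore the maximum dose. The lowest-to-highest ratio is exp{[logit(p_low) − logit(p_high)] / exp(mean log β)}. With (0.02, 0.1, 0.052), (0.1, 0.3, −0.176) and (0.001, 0.01, 0.362) it comes to 0.200 each time. A middle ratio of 0.4 reproduces the second row of Table 7.1:2 (mean 0.073, median 0.027).

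**Check of the prior.** Ratios 0.2 : 0.4 : 1 give prior means 0.054, 0.073 and 0.153, equal to Table 7.1:2, and P(rate ≥ 0.25) within 0.002 of the printed 0.050, 0.073 and 0.190.

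**Reproducing Table 10.3:3.** The printed results do not fit a 12-subject minimum. In scenario 3 only 0.2% of trials stopped and the printed minimum is 9 subjects, so a 12-subject rule would force a mean of at least 0.998 × 12 + 0.002 × 9 = 11.99; the table prints 9.32. Maxima reach 27, while the text states 18. Exact enumeration with cohorts of 3, skipping up to 500%, an MFD at 9 or more subjects with 6 at the dose, a maximum of 27, and the extra technical dose placed at twice the top dose (assumed) gives 94.8, 73.9, 99.4, 13.5 and 99.9% in the target range. Scenario 2 is furthest off, by 2.3 points; the Monte Carlo standard error is √(0.762 × 0.238 / 1000) = 1.35 points, so this is 1.7 standard errors.

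**Share in which the highest planned dose is declared MFD.** The written rule is taken as cohorts 3-3-6, next planned dose only, EWOC below 25%, at least 12 in total and 6 at the dose, maximum 18.

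| Scenario | True rate, highest dose | Printed target % | Highest dose, written rule % | Highest dose, 9/27 rule with skipping % |
|---|---|---|---|---|
| 1 | 0.153 | 94.1 | 69.2 | about 70 |
| 2 | 0.243 | 76.2 | 31.8 | about 37 |
| 3 | 0.053 | 99.0 | 96.2 | about 96 |
| 4 | 0.564 | 15.1 | 1.3 | about 3 |
| 5 | 0.243 | 99.9 | 55.0 | about 55 |

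In scenario 4 the highest dose is truly too toxic, and only the lowest dose (0.245) counts as target.

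**Sensitivity.** Cohorts of 3 throughout, otherwise as written, give 66, 29, 96, 1 and 55%. A middle ratio of 0.33 leaves the written-rule figures unchanged to the nearest point. Across the readings tried (9/27 with skipping, 12/18 with skipping, 12/18 next dose only), the top dose is declared in 66–72%, 29–39% and 49–55% of trials in scenarios 1, 2 and 5.

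**Hand check of scenario 5.** After 0/3 and 0/3, the posterior probability of overdose at the top dose is about 0.10 with 1 DLE in 6 (passes) and about 0.31 with 2 in 6 (fails). P(at most 1 of 6 at 0.243) = 0.757⁶ + 6 × 0.243 × 0.757⁵ = 0.188 + 0.362 = 55.1%. The lower doses are almost always clean, so the full enumeration gives nearly the same 55.0%. Another 44.9% of trials settle on the middle dose and are scored as correct.

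**The case against.** **The table is not wrong.** The appendix sets out to show precision in estimating the MFD, the column is labelled accordingly, and 7.6 speaks only of the MFD recommendation. This stands. A reader might infer that the sponsor claims an acceptable compound almost always reaches Part B; no sentence says so.

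**The SMC decides, not the model.** This also stands. A reader might take 69%, 32% and 55% as the probabilities that Part B opens. The documents do not support that: 3.1 gives no numeric cut-off, the MFD only *may* be considered reached, and 7.1 lets the SMC add subjects at the top dose. After two clean lower cohorts, 2 DLEs in 9 (overdose probability about 0.17) and 3 in 12 (about 0.23) pass EWOC although 2 in 6 does not. At a true rate of 0.243, P(at most 2 of 9) is 62% and P(at most 3 of 12) is 67%. The stops for two consecutive DLEs (3.1) and for serious or severe reactions (3.3.4.3) are not modelled here. The printed figures, however, also assume that the model is followed, so the same convention can be applied to the highest dose.

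**The comparison mixes two rules.** Partly right. The printed percentages fit a 9/27 rule with skipping. Under that rule the top-dose shares are still about 70, 37, 96 and 55%, so the gap comes mainly from the success metric. In scenario 2 about 5 points come from the rule.

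**A rate of 0.243 is borderline.** Overdose control is expected to hesitate there, and 10.3 calls the model conservative. But 7.1 places 0.243 inside the target interval, and scenario 1, at 0.153, still loses about 25 points. Scenario 3, at 0.053, loses only about 3.

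**Part A is largely past.** Protocol 1.2 reports seven treated subjects without a DLE, and SAP section 7 describes the BLRM analyses as performed. The point concerns how the design's performance is described, not its conduct.

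**Conclusion.** The concern holds as a reporting gap. Table 10.3:3 is correct for its stated metric, but that metric is not the decision Part A takes. With the written rule followed strictly, the highest dose is declared MFD less often than the printed target percentage by about 25 points in scenario 1 (94.1 − 69.2), 44 in scenario 2 (76.2 − 31.8), 3 in scenario 3 (99.0 − 96.2) and 45 in scenario 5 (99.9 − 55.0). Calling scenario 5 the best result does not fit a go/no-go on the highest dose when that dose is itself acceptable and nearly half the trials settle below it.

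These figures assume that all subjects are evaluable, that the SMC follows the model, six subjects at the first visit to the top dose, and the inferred dose ratios. They are conditional rates for the model rule, not forecasts of whether Part B opens.

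**What to change.** 1. Reconcile the simulation rule in 10.3 (increases up to 500%, results reaching 27 subjects and consistent with a 9-subject minimum) with the rule in 3.1 and 7.1 and the figures stated in 10.3 (next planned dose, 250%, at least 12 subjects, maximum 18). Then rerun the simulation under the reconciled rule.
2. Add to Table 10.3:3, for each scenario, the percentage of simulated trials in which the highest planned dose is declared MFD. Keep the existing columns.
3. Base the scenario conclusions, including the statement about scenario 5, and the statement in 7.6 on the new column. Use the sponsor's rerun values, not the approximations given here.
4. State beside the table that the SMC may depart from the model and may add subjects at the highest dose, so the column describes the model rule only.

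The cost is a simulation rerun, revised text in two sections, and less favourable stated figures. Conduct and patient numbers do not change.

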11. DESCRIPTION OF GLOBAL AMENDMENT(S)

11.1 GLOBAL AMENDMENT 1

Date of amendment		02 Jun 2021
EudraCT number		2020-005425-87
EU number		
BI Trial number		1451-0001
BI Investigational Medicinal Product(s)		BI 765128
Title of protocol		A First in Human trial to study safety and tolerability of single rising intravitreal doses (oPen label, non-randomized, uncontrolled) and in Addition the early biological Response of mulTiple intravitreal doses (double-masked, RandomIzed, sham-controlledD) of BI 765128 in panretinal photocoagulation (PRP) treated diabetic rEtinopathy (DR) patients with diabetic macular ischemia (DMI) – the PARTRIDGE Study
Global Amendment due to urgent safety reasons		
Global Amendment		
Section to be changed		Abbreviations
Description of change		Nrp1 – Neupilin 1 was added
Rationale for change		Clarification
Section to be changed		1.4.2.5, 3.1
Description of change		In part A the interval between dosing of subjects was extended.
Rationale for change		Authority feedback
Section to be changed		1.3
Description of change		Correction of the following sentence: The next higher dose will only be administered to the next cohort if the treatment in the preceeding dose cohort was safe and showed acceptable tolerability (see section 3.1).
Rationale for change		Clarification
Section to be changed		1.4.2.1
Description of change		The following sentence was deleted: There are no previous trials testing Neupilin-1 inhibitors in humans.
Rationale for change		Correction
Section to be changed		1.4.2.3
Description of change		Risks related to IVT injection regarding the use of material for intraocular drug delivery was updated.
Rationale for change		Following release of a caution statement by Becton Dickinson (BD), who supply materials for use in

		this trial, a risk-benefit evaluation and associated mitigation steps was performed and incorporated into the trial protocol.
Section to be changed		
Description of change		
Rationale for change		
Section to be changed		
Description of change		3.1, 7.1, 10.3
Description of change		The required number of subjects was corrected from 9 to 12 to the definition when the MFD may be considered reached.
Rationale for change		Correction
Section to be changed		3.3.3
Description of change		Exclusion criteria number 9 (part A) was revised to indicate that subjects enrolled in trial 1436-0001 SRD part may be enrolled into part A of this trial only after five half-lives since the last trial dose, if the participants were not discontinued from study due to safety reasons, and if no toxicity, adverse events or safety concerns related to the previous participation are present at the time of screening
Rationale for change		Authority feedback
Section to be changed		3.3.4.3
Description of change		The following sentence was added to clarify the re-start of the trial in case one of the stopping rules is triggered: "If the trial stops because one of the stopping rules is triggered, then the trial re-start will only be possible after regulatory authority approval via a substantial amendment."
Rationale for change		Authority feedback
Section to be changed		Section 3.1; Figure 3.1:2
Description of change		Word "safe" was removed from Figure 3.1:2 to be consistent with the statement on page 40 that Part B will not commence if the highest dose () is not considered safe and tolerable in Part A.

Rationale for change		Clarification
Section to be changed		Section 4.1.1; Table 4.1.1:2 Posology
Description of change		Reference to diluent in Part B was removed.
Rationale for change		Correction
Section to be changed		4.1.2
Description of change		The following sentence was revised as follows: The proposed escalation of the doses to [REDACTED] and [REDACTED] per eye is predicted to prolong the time for IVT antibody concentrations above the estimated minimally efficacious concentration, potentially allowing for longer dosing intervals. The starting dose and dose escalation were chosen based on the safety margin to the highest tested dose level [REDACTED] mg/eye) that did not result in adverse effects directly attributed to BI 765128 no observed adverse effect level (NOAEL), in the 13-week IVT toxicology study in cynomolgous monkeys.
Rationale for change		Correction
Section to be changed		4.2.2.3
Description of change		Word “condom” was added in brackets to the following sentence as an acceptable barrier method: WOCBP (for the definition please refer to Section 3.3.2) and men able to father a child must use two medically approved methods of birth control throughout the trial (from Visit 1 until End of Study visit) one barrier method (condom), and one highly effective non-barrier method.
Rationale for change		Clarification
Section to be changed		5.2.1
Description of change		DLE definition was revised to include the following event: Signs of vascular occlusion in a 1st (the main branch) or 2nd degree (the vessel after the first bifurcation of the main branch) retinal vessel, including peripheral retinal hemorrhages in the area supplied by the occluded vessel (hemorrhage of the macula would not be included as this is a symptom of the disease)
Rationale for change		Authority feedback
Section to be changed		5.2.4
Description of change		Option to use local lab for safety lab analysis was added if blood sampling for central lab at the trial site is not possible.
Rationale for change		Clarification
Section to be changed		5.3.2
Description of change		Correction of the following sentence: The samples may be used for further methodological

		investigations e.g. [REDACTED], to characterize [REDACTED] response or to address Health authority questions regarding the results/methodology; however, only data related to the analyte, and anti-drug antibodies, and mechanism of action will be generated by these additional investigations.
Rationale for change		Clarification
Section to be changed		[REDACTED]
Description of change		[REDACTED]
Rationale for change		[REDACTED]
Section to be changed		5.4
Description of change		The following sentences were added: “If feasible BI 765128 levels in [REDACTED] samples might be determined” “Additionally, if feasible proteins affected by the drug’s mode of action might be determined in serum samples”
Rationale for change		Clarification of additional measurements
Section to be changed		8
Description of change		Wording applicable for Germany was deleted.
Rationale for change		Germany will not participate in the trial.
Section to be changed		8.7
Description of change		“As deemed necessary” was added in brackets after participating investigator to clarify the role of the participating investigator in the SMC meetings.
Rationale for change		Clarification
Section to be changed		10.3
Description of change		The following sentence was corrected: The maximum allowed subject number for each trial was chosen as 1827 .
Rationale for change		Correction

11.2 GLOBAL AMENDMENT 2

Date of amendment		18 Jan 2022
EudraCT number		2020-005425-87
EU number		
BI Trial number		1451-0001
BI Investigational Medicinal Product(s)		BI 765128
Title of protocol		A First in Human trial to study safety and tolerability of single rising intravitreal doses (oPen label, non-randomized, uncontrolled) and in Addition the early biological Response of mulTiple

		intravitreal doses (double-masked, Randomized, sham-controlled) of BI 765128 in panretinal photocoagulation (PRP) treated diabetic retinopathy (DR) patients with diabetic macular ischemia (DMI) – the PARTRIDGE Study
Global Amendment due to urgent safety reasons		
Global Amendment		
Section to be changed		Synopsis, 3.3.2
Description of change		Part A, inclusion criteria # 5: BCVA was revised from ≤ 65 to 75 letters (20/50 to 20/32) in the study eye. Part B, inclusion criteria #5: BCVA was revised from ≤ 80 to 85 letters (20/25 to 20/20) in the study eye.
Rationale for change		To include a broader patient population on the study.
Section to be changed		3.3.2
Description of change		Part B, inclusion criteria 6 was revised: “Best-corrected VA in the non-study eye must be equal to or better than best-corrected VA in the study eye. If both eyes are eligible (per inclusion #5) and have identical best corrected VA, the investigator may select the study eye.” was replaced with “ If both eyes are eligible, the investigator may select either eye to be the study eye. ”
Rationale for change		Part B of the trial will only start if the highest dose is tolerated in part A. Once BI765128 has proved safe in part A, risks are low for the treated eye.
Section to be changed		Synopsis, 3.3.3
Description of change		Part A: Exclusion criteria#1: restriction of IVT injections for active DME (anti-VEGF, steroids) and macular laser decreased from 6 months to 3 months Exclusion criteria #2: restriction of anti-VEGF IVT injections for active DR decreased from 6 months to 3 months Part B: Exclusion criteria#2: restriction of IVT injections for active DME (anti-VEGF, steroids) and macular laser decreased from 6 months to 3 months Exclusion criteria#3: restriction of anti-VEGF IVT injections for active DR decreased from 6 months to 3 months

Rationale for change	To include a broader patient population participation on the study. Decreasing the restriction of the previous treatments from 6 months to 3 months is not expected to impact the results.
-----------------------------	--

11.3 GLOBAL AMENDMENT 3

Date of amendment	15 Jun 2022
EudraCT number	2020-005425-87
EU number	
BI Trial number	1451-0001
BI Investigational Medicinal Product(s)	BI 765128
Title of protocol	A First in Human trial to study safety and tolerability of single rising intravitreal doses (oPen label, non-randomized, uncontrolled) and in Addition the early biological Response of mulTiple intravitreal doses (double-masked, RandomIzed, sham-controlleD) of BI 765128 in panretinal photocoagulation (PRP) treated diabetic rEtinopathy (DR) patients with diabetic macular ischemia (DMI) – the PARTRIDGE Study
Global Amendment due to urgent safety reasons 	
Global Amendment 	
Section to be changed	Synopsis; Flow Chart I and II
Description of change	“including weight” included in brackets next to Physical examination
Rationale for change	Clarification in flow chart to indicate that weight is part of Physical examination.
Section to be changed	Synopsis; Flow Chart II, Tables 10.2:1 and 10.1:2
Description of change	Footnote in the Flowchart was revised as follows: See separate flow chart for [REDACTED], [REDACTED] sampling (Table 10.1: 2). PK samples during Visits 2, 3, & 4 should be taken within 30 min to 2hrs before drug administration. Tables: Time Point was revised as follows: Just Within 2 hrs before drug administration*. Footnote was deleted: *A time window of +/- 15 min for sample drawing is allowed.
Rationale for change	To allow broader time window for [REDACTED] samples before dosing.

Section to be changed		1.2.
Description of change		Data from clinical studies updated
Rationale for change		Update
Section to be changed		1.4.2.2
Description of change		The following sentence was revised as follows: Although no systemic adverse events were observed in the pre-clinical studies, at each time-point, subjects will undergo systemic evaluation as specified in the flow charts , including body weight, blood pressure, pulse rate, ECG and laboratory tests.
Rationale for change		Clarification
Section to be changed		1.4.2.5
Description of change		The following sentence was revised as follows: Additionally, a systemic evaluation will be performed at each the timepoints specified in the flow charts , to assess possible systemic reactions.
Rationale for change		Clarification
Section to be changed		3.3, 6.2.1
Description of change		The following sentences were revised: Section 3.3: Subjects who do not fulfil all eligibility criteria for a reason that later resolves and allows eligibility criteria to be met within a 12-week period after the initial screening visit, can be re-screened up to one time. Section 6.2.1: Subjects who do not fulfil all eligibility criteria and are screen failed for a reason that later resolves and allows eligibility criteria to be met within a 12-week period after initial screening visit , can be rescreened up to one time. For re-screening, subject must be registered in IRT, which will then provide a new subject number, and the subject must sign new Informed Consent Form (ICF). Imaging of retina (SD-OCT, OCTA, fundus photography) does not need to be repeated at the re-screening visit if the corresponding criteria for inclusion of the study eye were met at the initial screening visit and if the images are not older than 28 days at the re-screening visit; otherwise new images have to be performed.
Rationale for change		To remove the time restriction for rescreening of patients and allow patients beyond 12 weeks from date of initial screening to be rescreened once.
Section to be changed		3.3

Description of change		Update of the amounts of planned countries and sites
Rationale for change		Update
Section to be changed		3.3.3
Description of change		Part B: Exclusion criteria#7 removed: Clinically significant disorganisation of retinal inner layer (DRIL) in the study eye
Rationale for change		To broaden the subject population
Section to be changed		3.3.3
Description of change		Part B: Exclusion criteria 13 revised as follows: Previous participation in this trial or in other trials with IVT injections administered within 3 months of screening. Subjects enrolled in the sham arm of the MD part of trial 1436-0001 may be enrolled into Part B of this trial.
Rationale for change		Clarification
Section to be changed		6.2.1
Description of change		Revision as follows: Applies to the SRD part: In case of closed dose groups no further rescreening activities for a screened and eligible patient are required within 12 weeks after completed screening visit.
Rationale for change		Clarification to indicate that closed dose groups apply to Part A only.
Section to be changed		7.3.7
Description of change		Revision as follows: A preliminary analysis of [REDACTED] and [REDACTED] provided as individual values and geometric means of each cohort per dose level may be performed, if feasible.
Rationale for change		Clarification that in addition to PK parameters also a preliminary analysis of [REDACTED] may be performed.

11.4 GLOBAL AMENDMENT 4

Date of amendment		16 Mar 2023
EudraCT number		2020-005425-87
EU number		
BI Trial number		1451-0001
BI Investigational Medicinal Product(s)		BI 765128
Title of protocol		A First in Human trial to study safety and tolerability of single rising intravitreal doses (oPen label, non-randomized, uncontrolled) and in

		Addition the early biological Response of multiple intravitreal doses (double-masked, Randomized, sham-controlled) of BI 765128 in panretinal photocoagulation (PRP) treated diabetic retinopathy (DR) patients with diabetic macular ischemia (DMI) – the PARTRIDGE Study
Global Amendment due to urgent safety reasons		
Global Amendment		
Section to be changed		7.3.7 Interim Analyses
Description of change		Changing the fast track analysis data snapshot timepoint from V5 (Week 12) to V6 (Week 16) in Part B.
Rationale for change		Update made to ensure alignment with the PoCP criteria for the trial.
Section to be changed		Title page: Clinical Trial Leader
Description of change		Insertion of contact information for [REDACTED] and removal of contact information for [REDACTED]
Rationale for change		[REDACTED] has taken over the Clinical Trial Leader role from [REDACTED].

APPROVAL / SIGNATURE PAGE**Document Number: c34591878****Technical Version Number:6.0****Document Name: clinical-trial-protocol-version-05**

Title: A First in Human trial to study safety and tolerability of single rising intravitreal doses (oPen label, non-randomized, uncontrolled) and in Addition the early biological Response of mulTiple intravitreal doses (double-masked, RandomIzed, sham-controlleD) of BI 765128 in panretinal photocoagulation (PRP) treated diabetic rETinopathy (DR) patients with diabetic macular ischemia (DMI) - the

Signatures (obtained electronically)

Meaning of Signature	Signed by	Date Signed
Author-Clinical Trial Leader		17 Mar 2023 12:07 CET
Author-Trial Statistician		17 Mar 2023 12:24 CET
Approval		20 Mar 2023 13:01 CET
Verification-Paper Signature Completion		20 Mar 2023 13:17 CET

(Continued) Signatures (obtained electronically)

